Focal without clear observable signs	bny 40	Focal without clear observable signs	
Myoclonic	, 60, -	Myoclonic	
Absence/atypical absence	toe land sunde	Absence/atypical absence	
Infantile Spasms	Do olly	Infantile Spasms	
Epileptic Spasms	7	Epileptic Spasms	
Other	310	Other	

SEIZURE CLASSIFICATION - PRIMARY ENDPOINT

The primary endpoint for Study 1601 is defined as the change from baseline in seizures that result in drops. Seizures that result in drops include those of type: atonic, tonic, tonic/atonic, and tonic clonic (ie, generalized tonic clonic, and secondarily generalized tonic clonic). The seizures that result in drops are similar to those as defined in the Epidiolex Phase 3 clinical studies GWPCARE3 and GWPCARE4, which were atonic, tonic, or tonic clonic (Devinsky 2018, Thiele 2018).

Version 2.0

Syneos Health #1009529A

In the Statistical Analysis Plan (SAP) version 1.0 dated 5 August 2019, seizures resulting in drops were defined as those of the five types listed above and specified in the DSD as seizures that result in a fall based on a "Yes" response to Question 9 in the DSD. During study conduct a large number of data clarifications were raised for Question 9 leading to the conclusion that there was uncertainty amongst caregivers in how to properly answer the question. Based on this uncertainty, the definition of seizures that result in drops was changed to those of the five pre-specified types that have been reviewed and approved for each subject as a "drop seizure" by the Epilepsy Study Consortium (ESC). Approval is based on the seizures for each subject submitted to the ESC on the Seizure Identification Form during the Baseline Visit and logged in the eCRF on the Seizure History Form.

Thus, in version 1.1 of the SAP, drop seizures for the primary analysis will be those of the pre-specified type that have been approved for an individual subject as Drop by the ESC as indicated on the Seizure History eCRF under variable DROP_ and captured in the seizure diary.

Under this definition, classifying a particular seizure in the diary as a drop seizure requires determining whether the type of seizure in question has been identified in the Seizure History eCRF as a drop seizure for that subject. This can typically be done by matching a seizure type identifier in the diary to its counterpart in the Seizure History eCRF. Specifically, each seizure type entered into the Seizure History eCRF is identified by a "Record Position" number. These seizure types are then referred to by subjects or caregivers when recording seizures into the electronic Seizure Diary where they are labeled with a "Seizure Unique ID". For most subjects, there is a direct correspondence between the Seizure Unique ID in the seizure diary and the Record Position number on the Seizure History eCRF. However, for some subjects the correspondence is imperfect and aligning seizure types between the diary and the Seizure History eCRF requires an examination of text fields. In order to ensure that drop seizures are properly classified, a manual reconciliation between the Record Position number and the Seizure Unique ID was performed. The reconciliation resulted in a list of ESC-approved drop seizures for each subject from which the seizures entered in the DSD would be compared against in order to identify seizures for the primary endpoint. In order to facilitate seizure selection the list generated from the reconciliation was entered into a separate database and transferred to the study database via data transfer specifications.

The procedures for the reconciliation are described in an addendum to the Data Management Plan.

Statistical Analysis Plan for Cardiovascular Endpoints

Study Title: A Two-Part Study of ZX008 in Children and

Adults with Lennox-Gastaut Syndrome (LGS); Part 1: A Randomized, Double-blind, Placebocontrolled Trial of Two Fixed Doses of ZX008 (Fenfluramine Hydrochloride) Oral Solution as Adjunctive Therapy for Seizures in Children and Adults with LGS, Followed by Part 2: An Openlabel Extension to Assess Long-Term Safety of

ZX008 in Children and Adults with LGS

Investigational

Product:

ZX008

Sponsor Study No.: ZX008-1601

SAP Status: Final Version 1.1

Date of SAP: January 23, 2020

SAP Prepared by: ERT (Formerly Biomedical Systems)

Sponsor: Zogenix International Limited

A subsidiary of Zogenix, Inc. [name]

[figure not shown]

Table of Contents

3.2.6 Clinical Analysis of ECHOs
3.2.7 Alert Criteria

4.1 General Principles and Considerations	4 ST	ATISTICAL ANALYSIS22
4.2 Analysis Set	4.1	General Principles and Considerations
4.2.1 Handling of Missing Data	4.2	Analysis Set
4.3 Interim Analysis	4.7	2.1 Handling of Missing Data
4.4 Multiplicity Adjustments	4.3	Interim Analysis
4.5 Primary Analyses	4.4	Multiplicity Adjustments
4.5.1 Electrocardiogram	4.5	Primary Analyses
4.5.2 Echocardiogram	4.!	5.1 Electrocardiogram23
4.6 Secondary Analyses	4.!	5.2 Echocardiogram
4.7 Additional Analysis	4.6	Secondary Analyses
4.8 Categorical Analysis	4.7	Additional Analysis23
5 TABLES, FIGURES, AND LISTINGS	4.8	Categorical Analysis
6 REFERENCES 29 LINE CORPUTE ARTHUR	5 T#	ABLES, FIGURES, AND LISTINGS24
Zogenix ZX008-1601 SAP CONFIDENTIAL Page 4 of 30 January 23, 2020	6 DI	-FERENCES 20
Zogenix ZX008-1601 SAP Page 4 of 30 ERT CONFIDENTIAL January 23, 2020		cannot be lised and extens,
Zogenix ZX008-1601 SAP Page 4 of 30 ERT CONFIDENTIAL January 23, 2020	This good	inerit alication
ERI CONFIDENTIAL January 23, 2020	Zogenix 2	ZX008-1601 SAP Page 4 of 30
	ERT	CONFIDENTIAL January 23, 2020

Abbreviations and Definitions of Terms

Abbrevia	tions and Definitions of Terms	
ΔHR	Change from baseline in Heart Rate	
ΔΡR	Change from baseline in the PR-interval	"Notilation
ΔQRS	Change from baseline in the QRS duration	
ΔQTcF	Change from baseline in the QTcF interval	
ΔΔΗR	Change from baseline and placebo in Heart Rate	althor.
ΔΔΡR	Change from baseline and placebo in the PR-interval	
ΔΔQRS	Change from baseline and placebo in the QRS duration	D. J.
ΔΔQTcF	Change from baseline and placebo in the QTcF interval	9, (
ACI	Abnormal Clinically Insignificant	V6,
ANOVA	Analysis of Variance	
APCS	Abnormal Potentially Clinically Significant	
bpm	Beats per minute	
CAMI	Computer Assisted Measurement of Intervals	
C _{max}	Maximum Plasma Concentration	
CI	Confidence Interval	
DSF	Drop Seizure Frequency	
ЕСНО	Echocardiograms	
ECG	Electrocardiogram	
GSMB	Global Superimposed Median Beat	
kg	Kilogram	
HR	Heart Rate	
LGS	Lennox-Gastaut Syndrome	
mg	Milligram	
mm	Millimeter(s)	
mmHg	Millimeters of Mercury	
ms	Millisecond(s)	
PASP	Pulmonary Artery Systolic Pressure	
PR	Interval between the start of the P wave and start of the Q wave	
QRS	QRS waves complex on the electrocardiogram tracing	
QΤ	Interval between the start of the Q wave and the end of the T wave	
QTc	Corrected QT duration	
QTcF	QT interval corrected using Fridericia's formula	

RR	The time interval between consecutive heart beats.
SAP	Statistical Analysis Plan
SD	Standard Deviation
STP	Stiripentol
TdP	Torsade de Pointes
VHD	Valvular heart disease
ZX008	Fenfluramine Hydrochloride

Ruffly Copy of Support Support

1 Introduction

Study ZX008-1601 is investigating ZX008, an oral solution of fenfluramine hydrochloride, for the treatment of seizures associated with Lennox-Gastautsyndrome.Lennox-Gastaut syndrome is a rare epileptic encephalopathy. The onset of Lennox-Gastaut syndrome occurs most commonly before age 11, with a peak between 3 and 5 years of age (Arzimanoglou 2009; Hancock 2013). Patients with Lennox-Gastaut syndrome account for 5 to 10% of children with seizures (Panayiotopoulos 2005). The most common seizure types are generalized tonicclonic seizures, tonic seizures, atonic seizures, and tonic/atonic seizures, all of which most often can result in "drop attacks." Other seizure types that occur in some Lennox-Gastaut syndrome patients include atypical absences, nonconvulsive seizures, focal seizures, and myoclonic seizures. Nearly all patients have treatmentresistant, lifelong epilepsy. Patients with Lennox-Gastaut syndrome have a poor prognosis: 5% of children die, 80 to 90% continue having seizures into adulthood, and nearly all have cognitive and behavioral problems (Panayiotopoulos 2005). Children and adults with Lennox-Gastaut syndrome have an enormous impact on their families and efforts to improve the quality of life for these subjects are complex.

Fenfluramine is a serotonin releasing agent and increases the availability of extracellular serotonin by binding to the serotonin transporter protein and by being taken into the nerve terminal, where it disrupts vesicles, causing a release of serotonin into the extracellular space. It reverses the serotonin transporter function to promote serotonin release rather than uptake. In vivo and in vitro studies conducted by Zogenix suggest that fenfluramine reduces seizures by acting as an agonist at the 5-HT1D and 5-HT2C receptors and by acting as a positive allosteric modulator on the sigma-1 receptor; studies have shown positive allosteric modulators of sigma-1 reduce seizures in animal models. Fenfluramine may also exert antiseizure activity through the 5-HT1A and 5-HT2A receptors and possibly other yet to be identified mechanisms.

When fenfluramine was marketed for treatment of obesity at doses of 60-120 mg/day, reports of cardiac valvular disease emerged (Connolly, 1997). The FDA issued an advisory request for information from similar cases and eventually requested voluntary withdrawal of fenfluramine and dexfenfluramine from the market in 1997.

Valvular heart disease (VHD) and pulmonary arterial hypertension (PAH) are important potential risks to monitor with ZX008 treatment based on the previously reported cardiotoxicity associated with fenfluramine treatment for adult obesity, commonly in combination with phentermine, at doses of 60 to 120 mg/day: ie, 2 to 4 times higher than the proposed maximum daily dose for Dravet syndrome and Lennox-Gastaut syndrome. The ZX008 clinical development program includes a prospectively-defined, long-term longitudinal cardiovascular study of the function and structure of the heart valves, focusing on signs of VHD and PAH. Safety assessment in the ZX008 clinical program includes serial color Doppler ECHOs to monitor for VHD (valvulopathy) and PAH. Study 1603, a thorough QT study in healthy adult subjects was also conducted.

In addition to Lennox-Gastaut syndrome, Zogenixis investigating ZX008 for the

treatment of seigres associated with Drayet syndrome. Zogenix has reported safety and efficacy data from 2 adequate and well controlled studies in patients with Dravet syndrome, Study 1 and Study 1504 Cohort 2, and 1 interim analysis from the open-label extension study (Study 1503). Study 1 compared 2 doses of ZX008, 0.2 mg/kg/day and 0.8 mg/kg/day (up to a maximum of 30 mg/day), to placebo in subjects receiving standard of care anti-epileptic treatments excluding stiripentol (STP). Study 1504 Cohort 2 compared a dose of ZX008 0.5 mg/kg/day (up to a maximum of 20 mg/day) to placebo in subjects receiving standard of care anti-epileptic treatments where administration of STP (in combination with clobazam [CLB] and/or valproate [VPA]; ie, the STP regimen) was mandatory.

authorization, see a see Both studies met the primary efficacy endpoint and all key secondary efficacy endpoints. In both studies, a highly statistically significant reduction in monthly convulsive seizure frequency was achieved in subjects randomized to receive ZX008 in addition to their standard of care antiepilepsy treatments compared to placebo. Results from both Phase 3 studies demonstrated that ZX008 was and well tolerated at doses up to 30 mg/day administered in the ZX008 clinical program.

A prospectively-defined cardiovascular monitoring program that employed color Doppler echocardiography (ECHO) was implemented in the ZX008 clinical program (all Dravet syndrome and Lennox-Gastaut syndrome [LGS] trials) to monitor for valvular heart disease (VHD) or pulmonary artery hypertension (PAH), this ECHO program was designed with input from FDA and from cardiology experts.

No VHD, as measured by valve function and observations of valve structure, or PAH, as measured by pulmonary pressure, has developed in any subject in the reported Dravet syndrome trials, nor in fact has any VHD or PAH developed in any subject in the program as of July 2019. Normal nonpathologic trace and mild mitral regurgitation and trace aortic regurgitation were observed in very low rates consistent what has been reported in literature with no subjects progressing to VHD; most of these findings were transient and fluctuated between absent and trace requigitation during the study. The point prevalence of trace mitral and aortic regurgitation were equal to or lower than the incidence rates reported in normal healthy developing children (Webb 2015).

This Statistical Analysis Plan (SAP) for Cardiovascular Endpoints outlines the planned analyses to support the assessment of electrocardiographic (ECG) and echocardiographic data for Part 1 of the trial. The planned analyses identified in this SAP may be included in regulatory submissions, and exploratory analyses not defined in this SAP may be performed to support a more thorough understanding of the safety data. All post-hoc or unplanned analyses performed not identified in this SAP will be documented.

Documents used to develop this SAP are:

- Study Protocol ZX008-1601 (29July 2019, Amendment 2.1).
- Syneos Health-ZogenixZX008-1601Statistical Analysis Plan (Final Version 1.0, 5August 2019).
 - ZX008 Investigational Brochure (Version 7.0, July 2019).

The description of methodology of analysis for Part 2 of the study will be provided

This document cannot be used any extensions of variations the real and any extensions of variations are variations.

2 Study Design and Cardiovascular Analysis Objectives

2.1 General Design and Plan

Study ZX008-1601 is an international multicenter study being conducted in two parts. Up to approximately 80 study sites in North America, Europe, Australia, and Japan are planned to participate. Part 1 is a double-blind, parallel-group, placebocontrolled, study to assess the efficacy and safety of two doses of ZX008 when used as adjunctive therapy for seizures in children and adult subjects with Lennox-GastautSyndrome(LGS). Part 1 will include 2 cohorts: Cohort A will include randomized subjects from North America, Europe, and Australia; Cohort B will include randomized subjects from Japan.Part 2 is an open-label extension to assess long-term safety of ZX008.

Each subject in Part 1 is assigned to one of 2 treatments (0.2 mg/kg or 0.8 mg/kg) or placebo groups. Treatments were assigned on a 1:1:1 basis.

Data from Part 1, Cohort A for cardiovascular endpoints will be analyzed. All other study results for these subjects (demographics, efficacy, safety, PK) will be presented in the Clinical Study Report for ZX008-Study 1601 Part 1.

Electrocardiograms (ECGs) and echocardiograms (ECHOs) are being analyzed by ERT (formerly Biomedical Systems (St. Louis, MO)).

All ECGs will be reviewed and interpreted by a board-certified cardiologist.

Echocardiograms will be reviewed by two, board-certified cardiologists. In the case of a discrepancy between the readers, the echocardiogram was sent to adjudicatorsfor final reading. At the initiation of the ZX008 Program, the International (Pediatric) Cardiology Advisory Board (ICAB) was set-up to oversee the vendor's ECHO readings. ICAB members were chosen solely based on their academic credentials and experience, with the Chair being chosen based upon his/her seniority and respect in the field of echocardiography. When there is a differing interpretation of findings in an ECHO of any subject between the vendor and ICAB (either in the alert level of valvular regurgitation or presence or absence of pulmonary hypertension), the following process will occur: a telephone conference call will be held with the vendor ERT cardiology readers and ICAB reader and ICAB Chair (if the Chair was reader, then only he/she will be on call) to discuss the ECHO findings and try to come to an agreement on interpretation; if agreement cannot be reached then ICAB Chair will read the ECHO and his/her reading will become the official reading. This one ECHO report will then be sent to the IDSMC.

2.2 Objectives

The primary objective of ZX008-1601 Part 1is to demonstrate that ZX008 0.8 mg/kg/day is superior to placebo as adjunctive therapy in the treatment of uncontrolled seizuresin children and adults with Lennox-Gastaut syndrome (LGS) based on the change in frequency of seizures that result in drops (drop seizure frequency,DSF) between baseline and the combined Titration and Maintenance Periods (T+M).

2.2.1 Cardiovascular Safety Objectives

The primary cardiovascular safety objective of this analysis is to evaluate the effect of ZX008 on the heart as demonstrated by ECHO.

Variables included in the analysis are listed below. These will be compared between Placebo and the 0.2 mg/kg and 0.8 mg/kg groups independently.

2.3 Endpoints

2.3.1 Echocardiograms

2.3.1.1 Main Focus for Echocardiograms

The main focus for the echocardiographic analysis is the regurgitation score for the mitral and aortic valves at each time-point with the main focus being the development of clinically meaningful (pathologic) changes in valve regurgitation (definitions and thresholds defined below).

- Number of subjects who meet the FDA case definition of drug associated valvulopathy-aortic regurgitation ≥ mild and/or mitral regurgitation ≥ moderate
- Number of subjects with ≥ trace mitral or aortic regurgitation at least one time post-baseline
- Number of subjects with ≥ trace mitral or aortic regurgitation at end of study
- Number of subjects within each mitral or aortic regurgitation score by visit
- Number of subjects with clinically confirmed Valvular heart disease (VHD)

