2.3.1.2 Other Echocardiographic Analyses

Other, secondary endpoints include:

- Number of subjects within each tricuspid or pulmonic regurgitation score by visit
- Number of subjects with normal ortrace tricuspid or pulmonic regurgitation at baseline and ≥ mild tricuspid or pulmonic regurgitation at end of study
- Pulmonary Artery Systolic Pressure (PASP)
 - o Mean change from baseline at end of study
 - Mean maximum change from baseline at anytime during therapy
 - Number of subjects with change from baseline at anytime during therapy shows:
 - > 10 mmHg
 - >15 mmHg
 - >20 mmHg

Number of subjects at anytime during therapy shows

- PASP>35 mmHg
- Right ventricular outflow tract(RVOT) (will be used only as confirmatory variables for pulmonary hypertension)

- o Mean Change from Baseline in RVOT (mmHg) by visit
- Number of patients with Baseline ≥100 msec and at EOS/ET RVOT
 <100 msec
- Number of patients with any RVOT measurement < 100 msec postbaseline

Summary of the number of ECHOs per subject will also be presented.

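### The mitral and aortic valve endpoints ignore the screening ECHO, so they mix pre-existing with new regurgitation although the stated focus is its development

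*SAP*

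**What the plan says.** Section 2.3.1.1 of the Cardiovascular SAP frames the mitral and aortic analysis with "the main focus being the development of clinically meaningful (pathologic) changes in valve regurgitation". Section 4.1 names the development of valvular heart disease (VHD) and pulmonary hypertension as the primary outcome, and 4.5.2 repeats that aim.

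Section 2.3.1.1 then lists five counts:

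- the FDA case definition: mild or worse at the aortic valve, moderate or worse at the mitral valve, or both;
- "Number of subjects with ≥ trace mitral or aortic regurgitation at least one time post-baseline";
- the same grade threshold applied to the end-of-study ECHO;
- subjects in each regurgitation score by visit;
- subjects with clinically confirmed VHD.

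For the less central valves, section 2.3.1.2 uses a different form: "Number of subjects with normal ortrace tricuspid or pulmonic regurgitation at baseline and ≥ mild tricuspid or pulmonic regurgitation at end of study". Section 3.2.4 fixes the ECHO baseline as the screening ECHO. In section 5, Tables 4.1 and 4.2 (mitral and aortic) are titled as point prevalence.

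**The concern.** Development means a change from a starting state, and none of the five mitral/aortic counts refers to that state. The Introduction to the Cardiovascular SAP makes carriers at screening plausible. For the sponsor's Dravet trials it states: "Normal nonpathologic trace and mild mitral regurgitation and trace aortic regurgitation were observed". It adds that most such findings came and went between absent and trace.

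Two things follow. Subjects who already had the finding enter the count in every arm and pull the arms' proportions together in relative terms. A chance difference between arms in screening findings also passes into the post-baseline counts, where it can look like harm or hide it. Valve disease is a named potential risk of this drug, so the main valve summary should separate new from old findings.

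**Working it through.** **Step 1. Which ECHO endpoints refer to the screening state?**

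| Endpoint | Section | Baseline condition |
|---|---|---|
| FDA case definition | 2.3.1.1 | None; does not say new or post-baseline |
| At least trace, any post-baseline ECHO | 2.3.1.1 | None |
| At least trace, end of study | 2.3.1.1 | None |
| Score by visit | 2.3.1.1 | None; cross-sectional |
| Clinically confirmed VHD | 2.3.1.1 | None stated; clinical threshold |
| Tricuspid/pulmonic at least mild, end of study | 2.3.1.2 | Normal or trace at baseline |
| RVOT below 100 ms, end of study | 2.3.1.2 | At least 100 ms at baseline |
| PASP | 2.3.1.2 | Change from baseline |

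The secondary variables are tied to baseline and the principal valves are not. No reason is given.

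**Step 2. Is the gap filled elsewhere?** Section 4.1 promises changes from baseline for ECG and ECHO variables in general. Section 4.8 promises categorical changes as set out in section 2.3, but 2.3 sets out none for the mitral or aortic valve. Section 4.5.2 plans category counts by regimen and visit. No title in section 5 names a mitral or aortic shift or a new-onset count. The heat maps (2.3.1.3) show Visit 1 beside later visits for each subject, but no rule turns them into an incidence by arm.

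**Step 3. Illustration of size.** There is no plan figure to reproduce, since section 2.4.1 states that no cardiac sample size was calculated. The only input from the plan is n = 79 per arm, the efficacy sample size in 2.4.1. Everything else is assumed:

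- q, the proportion with the finding at screening: 5%, 10%, 20%;
- new-onset risk i: 5% on placebo, 15% on active;
- r, the probability that a carrier is still positive post-baseline: 1 at first.

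Proportion counted as the plan is written: p = q·r + (1 − q)·i.

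At q = 10%, r = 1: placebo 0.10 + 0.90 × 0.05 = 0.145; active 0.10 + 0.90 × 0.15 = 0.235; ratio 0.235/0.145 = 1.62; difference 0.090; pre-existing share of the placebo count 0.10/0.145 = 69%.

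| q | Placebo | Active | Difference | Ratio as written | Ratio, conditioned | Pre-existing share, placebo / active |
|---|---|---|---|---|---|---|
| 5% | 9.8% | 19.3% | 9.5 points | 1.97 | 3.0 | 51% / 26% |
| 10% | 14.5% | 23.5% | 9.0 points | 1.62 | 3.0 | 69% / 43% |
| 20% | 24.0% | 32.0% | 8.0 points | 1.33 | 3.0 | 83% / 62% |

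The difference is (1 − q) × 10 points, so it keeps its sign. At q = 0 the two definitions coincide.

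As a gauge of information lost (no valve test is specified), approximate power of a two-sided 5% comparison is 0.40, 0.30 and 0.20 as written. Conditioned on screening, with n = 79(1 − q), it is 0.53, 0.51 and 0.47.

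**Step 4. Partial persistence.** Take r = 0.5. At q = 10%: placebo 0.05 + 0.045 = 0.095; active 0.05 + 0.135 = 0.185; ratio 1.95. At q = 20%: 0.10 + 0.04 = 0.14 and 0.10 + 0.12 = 0.22; ratio 1.57. The dilution is smaller but remains.

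**Step 5. Chance imbalance in carriers.** The 95% range for the between-arm difference is ±1.96 × √(2q(1 − q)/79): ±6.8, ±9.4 and ±12.5 points at q = 5%, 10% and 20%. It carries over in full only if r = 1; at r = 0.5 and q = 10% the carried-over part is about 9.4 × 0.5 = 4.7 points.

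**The case against.** A reader might infer that the endpoints cannot answer the question of development at all. The documents do not support that. Section 2.2.1 compares each dose with concurrent randomised placebo, so the unconditioned counts remain a fair between-arm contrast, and Step 3 shows the difference shrinking only by the factor 1 − q.

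Other points also stand in part:

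- Two of the five counts, the FDA case definition and confirmed VHD, use pathologic or clinical thresholds, so it would be wrong to say that all the main endpoints count any regurgitation.
- Baseline cases at the FDA threshold may be few. The main SAP (section 4, and note n to Table 4) puts an ECHO before randomisation. The eligibility criteria are in the protocol, which is not at hand, so it is unknown whether they exclude such cases or reach down to trace.
- The Introduction reports very low rates in the Dravet trials, so the upper end of the assumed prevalence has no support here, and the fluctuation it describes argues against full persistence.
- By-visit scores and heat maps let a reader see a screening imbalance, and the shells of the tables that support the heat maps are not shown.
- One absent screening ECHO does not prove that a later trace finding is new.

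None of this supplies a definition of new or worsened mitral or aortic regurgitation. The last point limits how much weight new trace findings should carry; the placebo arm shows how often they arise without drug.

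**Conclusion.** The concern holds in a limited form. The two counts of at least trace regurgitation and the FDA case-definition count are not conditioned on the screening ECHO. They therefore mix pre-existing with new findings and do not match the plan's own focus on development, while section 2.3.1.2 shows that the authors use such a condition elsewhere. The consequence is dilution of a valid randomised comparison, not invalidity.

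The size depends on screening prevalence and persistence, which the documents do not give. Under the assumptions above, a threefold risk of new onset shows as a ratio between 1.97 (q = 5%) and 1.33 (q = 20%) with full persistence, and as 1.95 at q = 10% if half the carriers revert. If screening findings are very rare, the effect is negligible. The case for change rests on the mismatch with the stated question and on the low cost of repair, not on any one of these figures.

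**What to change.** In section 2.3.1.1, and alongside Tables 4.1 and 4.2, add by arm and separately for the mitral and aortic valves:

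- a shift table from screening grade to worst post-baseline grade and to end-of-study grade, with the number and percentage worsening by at least one grade;
- new-onset counts, with subjects below the threshold at screening as denominator, for at least trace and for the FDA case definition (mitral and aortic components).

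Keep the pathologic-threshold endpoints as the main focus and condition the case-definition count on screening. Report new trace findings as supportive, because trace fluctuates. Keep the prevalence tables as descriptive.

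The cost is one or two more tables from data already collected, and a slightly smaller denominator for the new-onset counts (for example 79 × 0.90 ≈ 71 per arm if 10% are carriers).
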